9. EFFICACY ANALYSES

9.1. Definition of the Primary Efficacy Endpoint

The primary efficacy endpoints include:

- Percentage change from baseline in total IgG at Week 7.

Supportive variables to the primary efficacy laboratory variable are:

- Percentage change from baseline in IgG1 at Week 7
- Percentage change from baseline in IgG2 at Week 7
- Percentage change from baseline in IgG3 at Week 7
- Percentage change from baseline in IgG4 at Week 7
- Percentage change from baseline in anti-AChR-IgG level at Week 7

Percentage change from baseline will be calculated as:

$$\% \Delta = \left[100 \times \left(\frac{\text{Week 7} - \text{Baseline}}{\text{Baseline}} \right) \right]$$

9.2. Statistical Hypotheses for the Efficacy Endpoints

The efficacy endpoint hypotheses will be tested in the order below.

1. $H_0: \mu_{11} = \mu_{1p}$ vs. $H_A: \mu_{11} \neq \mu_{1p}$, where μ_{11} = LSmean of $\% \Delta_{\text{Total IgG}}$ for RVT-1401 680 mg/wk or RVT 340 mg/wk and μ_{1p} = LSmean of $\% \Delta_{\text{Total IgG}}$ for placebo

Supportive superiority on percent change in IgG is evaluated:

- H_{01} : The percent change from baseline in Total IgG after 6 weeks of treatment for the group treated with RVT-1401 680 mg/wk is equal to that of the placebo group.
- H_{11} : The percent change from baseline in IgG after 6 weeks of treatment for the group treated with RVT-1401 680 mg/wk is not equal to that of the placebo group.

Supportive superiority on percent change in IgG is evaluated:

- H_{02} : The percent change from baseline in IgG after 6 weeks of treatment for the group treated with RVT-1401 340 mg/wk is equal to that of the placebo group.
- H_{12} : The percent change from baseline in IgG after 6 weeks of treatment for the group treated with RVT-1401 340 mg/wk is not equal to that of the placebo group.

Superiority on percent change in anti-AChR-IgG level is evaluated:

- H_{03} : The percent change from baseline in *anti-AChR-IgG* after 6 weeks of treatment for the group treated with RVT-1401 680 mg/wk is equal to that of the placebo group.
- H_{13} : The percent change from baseline in *anti-AChR-IgG* after 6 weeks of treatment for the group treated with RVT-1401 680 mg/wk is not equal to that of the placebo group.

evaluation continues:

- H_{04} : The percent change from baseline in *anti-AChR-IgG* after 6 weeks of treatment for the group treated with RVT-1401 340 mg/wk is equal to that of the placebo group.
- H_{14} : The percent change from baseline in *anti-AChR-IgG* after 6 weeks of treatment for the group treated with RVT-1401 340 mg/wk is not equal to that of the placebo group.

Conditional on the p-value being less than alpha, testing continues:

Superiority on change in MG-ADL is evaluated:

- H_{05} : The percent change from baseline in *MG-ADL* after 6 weeks of treatment for the group treated with RVT-1401 680 mg/wk or RVT 340 mg//wk is equal to that of the placebo group.
- H_{15} : The percent change from baseline in *MG-ADL* after 6 weeks of treatment for the group treated with RVT-1401 680 mg/wk or RVT-1401 340 mg/wk is not equal to that of the placebo group.

Conditional on the p-value being less than alpha, testing continues:

- H_{06} : The proportion of responders on *MG-ADL* after 6 weeks of treatment for the group treated with RVT-1401 680 or 340 mg/wk is equal to that of the placebo group.
- H_{16} : The proportion of responders on *MG-ADL* after 6 weeks of treatment for the group treated with RVT-1401 680 or 340 mg/wk is not equal to that of the placebo group.

9.3. Analysis of the Primary Efficacy Endpoint

The primary efficacy endpoints will be summarized descriptively (sample size, mean, standard deviation, median, Q1, Q3, minimum and maximum). Efficacy analysis will be done on the FAS subjects consistent with ICH E9 principles.

The primary hypothesis test analysis will use the intent-to-treat methodology and a main-effects model for ANCOVA, with adjustment for baseline levels. If 2 or more subjects have missing Week 7 data, missing data will be predicted using MI methodology.

For sensitivity analysis, interaction terms of site by treatment group will be examined. In the event of a significant interaction term, the impact on analysis conclusion will be examined. The primary analysis model will not include interaction terms. Assumptions underlying ANCOVA will be examined. If assumptions of ANCOVA are unwarranted and the validity of the ANCOVA becomes questionable, rank analogues will be advanced as the primary analysis. Missing data will be managed using MI methods.

The primary analysis on treatment responders will use Fisher's exact test supported by logistic regression with baseline measure as covariates.

The primary analysis will be conducted using the FAS following the intent-to-treat (ITT) principle.

Descriptive summaries will be produced for the actual values, change from baseline and percent change from baseline by treatment group and visit.

Longitudinal data analyses will be used to support the primary analysis utilizing a mixed model repeated measures (MMRM) methodology with treatment, baseline as covariate, time, treatment-by-time interaction as fixed effects, and subject as a random effect.

For completeness, an observed cases analysis will be done by visit in which no data are excluded, no data are imputed, and no data are represented at times other than when they were observed. As an alternative for handling missing data according to the rules of the primary analysis, a sensitivity analysis will be done using LOCF.

For statistical analyses, 95% confidence intervals will be produced for the least squares means (LSM) in each treatment group and combined treatment group, as well as the LSM differences as compared to placebo. For MMRM and ANCOVA, two-sided p-values will be displayed for the comparison against placebo.

To ensure robustness of analysis conclusions against parametric assumptions, rank analogues will be executed as sensitivity analysis. If the PPS differs from the FAS by more than 10%, the analyses will be replicated on the PPS. If the PPS and the FAS do not differ by more than 10%, analysis may not be done on the PPS. Final judgments will be made at the blinded data review meeting in accordance with ICH E9.

All analyses will be done using the intent-to-treat (ITT) principle.

9.4. Secondary Efficacy Endpoints

9.4.1. Definition of Secondary Efficacy Endpoints

Secondary efficacy endpoints include:

- Change from baseline in the MG-ADL score by visit through Week 7

- Achievement of MG-ADL response of 2 points or more at Week 7
- Change from baseline in the QMG score by visit through Week 7
- Achievement of QMG improvement with an improvement from baseline on the QMG score by ≥ 3 points at Week 7
- Achievement of MGC improvement with an improvement from baseline on the MGC score by ≥ 3 points at Week 7
- Change from baseline in the MGC score by visit through Week 7
- Change from baseline in the MG-QOL15r score by visit through Week 7
- Durability of MG-ADL response as evaluated by proportion of assessments by Week 7 with change showing improvement of 2 or more points.
- Durability of QMG response as evaluated by proportion of assessments by Week 7 with change showing improvement of 3 or more points.
- Durability of MGC score as evaluated by proportion of assessments by Week 7 with change showing improvement of 3 or more points.
- Achievement of improvement by meeting at least one of the following criteria:
 - Achievement of improvement of at least 2 points on MG-ADL
 - Achievement of improvement of at least 3 points on QMG
 - Achievement of improvement of at least 3 points on MGC
- Achievement of improvement by meeting at least two of the following criteria:
 - Achievement of improvement of at least 2 points on MG-ADL
 - Achievement of improvement of at least 3 points on QMG
 - Achievement of improvement of at least 3 points on MGC
- Achievement of improvement by meeting all three of the following criteria:
 - Achievement of improvement of at least 2 points on MG-ADL
 - Achievement of improvement of at least 3 points on QMG
 - Achievement of improvement of at least 3 points on MGC

The QMG scale is comprised of 13 items that are graded on a scale of 0 to 3. The sum across all 13 items represents the QMG score which will range from 0 to 39.

The MGC scale is a patient reported scale comprised of 10 items that are rated on a scale ranging from 0 to 9 depending on the item. The sum across all 10 items represents the total MGC score which will range from 0 to 50.

The MG-ADL is a patient reported questionnaire comprised of 8 items that are rated on a scale of 0 to 3. The sum across all 8 items represents the MG-ADL score which will range from 0 to 24.

The MG-QOL15r is a patient-reported scale comprised of 15 items that are graded on a scale of 0 to 2. The sum across all 15 items represents the MG-QOL15r score which will range from 0 to 30.

Missing individual items or questions from the QMG scale, MGC scale, the MG-ADL questionnaire, and the MG-QOL15r scale will be imputed using the method of LOCF if no more than 2 questions are missing for QMG scale, MGC scale, and MG-QOL15r scale or no more than 1 question is missing for the MG-ADL questionnaire. Otherwise, will take the total score for the given scale as missing.

[figure not shown]
9.4.2. Analysis Methods for Secondary Efficacy Endpoints

[figure not shown]
Total MG-ADL, QMG, MGC, and MG-QoL15r score and each of the component scores will be summarized descriptively (sample size, mean, standard deviation, median, Q1, Q3, minimum and maximum) by treatment group and analyzed using ANCOVA model with treatment as a fixed factor and baseline value as a covariate. Least-squares means and 95% CIs will be calculated and provided for each treatment group. The least-squares means will be compared using a t-test.

Number and proportion of subjects with a ≥ 2 -, ≥ 3 -, ≥ 4 -, ≥ 5 -, ≥ 6 -, ≥ 7 -, or ≥ 8 -point improvement in total MG-ADL, QMG, and MGC score at all timepoints will be summarized descriptively by treatment group. The percentage will be calculated using those participants who had a value at the time point. Fisher's exact test will be used to compare each active dose regimen to placebo. A logistic regression with treatment as the main effect and the baseline value as a covariate will be used for comparing the proportion of responders between the treatment groups. The odds ratio and corresponding 2-sided 95% Wald confidence interval will be provided.

There will be no adjustments for multiple comparisons for secondary endpoints. An alpha level of 0.05 will determine statistical significance. Analyses of secondary efficacy endpoints will be provided for the FAS.

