5.4. Multiple Comparisons

Adjustments for multiple comparisons for the primary efficacy endpoints list in Section 9.2 will be performed using a fixed, sequential testing procedure. The order of the testing sequence is specified in Section 9.2. The first test in the sequence will be performed at a significance level of 0.05. If that test is significant, then the second test in the sequence will be performed at a significance level of 0.05, and so on. Testing will stop when a non-significant test occurs in order to maintain a family-wise error rate of alpha=0.05.

There will be no adjustments for multiple comparisons for the secondary efficacy or OLE endpoints.

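### Fisher's test for the MG-ADL responder hypothesis (H06) is valid but can use at most 2.2% of its 5% alpha at the planned sizes; a pre-specified exact unconditional test would be a cheap gain in power

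*SAP*

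**What the plan says.** SAP 9.3: "The primary analysis on treatment responders will use" Fisher's "exact test supported by logistic regression with baseline measure as covariates".

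SAP 9.2 ends its ordered list with H06, whose null states equality with placebo: "The proportion of responders on *MG-ADL* after 6 weeks of treatment for the group treated with RVT-1401 680 or 340 mg/wk is equal to". The alternative is two-sided: "treated with RVT-1401 680 or 340 mg/wk is not equal to that of the placebo group". SAP 9.4.1 sets MG-ADL response at 2 points or more at Week 7.

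SAP 5.4 gives each test in the sequence 0.05: "Testing will stop when a non-significant test occurs in order to maintain a family-wise error rate of alpha=0.05".

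SAP 9.4.2 covers the secondary responder endpoints. There Fisher's "exact test will be used to compare each active dose regimen to placebo", without multiplicity adjustment: "An alpha level of 0.05 will determine statistical significance".

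Protocol 10.3.2 also names Fisher's test for categorical secondary endpoints and allows the two active arms to be combined. The planned size is 14 active and 7 placebo (SAP 1.3), randomised 1:1:1 (SAP 1.2), so 7 per arm. Neither document gives a response rate, a power or an attained level for any responder test.

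**The concern.** Fisher's test conditions on the total number of responders. With 21 participants few p-values are attainable, and the largest one not above 0.05 is often well below it. The test then rejects less often under the null than its allotted 5%, and power is lost.

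At stake is the chance of supporting the clinical responder question at the end of the sequence. SAP 8.3 gives treatment responsiveness co-primary importance, so the question is not peripheral. An exact unconditional test also guarantees the 5% limit, and the loss can be partly avoided if such a test is named in advance.

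**Working it through.** **Inputs.** Sizes 14 vs 7 and 7 vs 7 (SAP 1.2, 1.3); two-sided alpha 0.05 (SAP 5.4, 9.2). Response rates are assumptions. The plan has no responder figure to reproduce; its only power statement concerns percentage change in IgG.

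**Formulas.** With a of n1 active and b of n2 placebo responders, and rates pA and pP, a table has probability

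C(n1,a) pA^a (1−pA)^(n1−a) × C(n2,b) pP^b (1−pP)^(n2−b).

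- Maximum size: sum this over all rejected tables with pA = pP = p, then maximise over p.
- Power: the same sum at the assumed pA and pP.
- Boschloo p-value: take all tables with a two-sided Fisher p no larger than the observed one, sum their probabilities at a common p, and maximise over p.

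**Fisher, 7 vs 7.** With active better, it rejects 5–0, 6–0, 6–1, 7–0, 7–1 and 7–2. The size peaks at p = 0.5, where each table's probability is its number of arrangements divided by 2^14. Arrangements: 21 + 7 + 49 + 1 + 7 + 21 = 106. Doubling for the other direction gives 212/16,384 = 1.29%.

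**Fisher, 14 vs 7.** For 0, 1, 2, 3 or 4 placebo responders it needs at least 7, 10, 12, 13 or 14 active responders. The size peaks at 2.21%, at a common rate near 40%.

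**Boschloo, 14 vs 7.** The thresholds become 6, 9, 11, 13 and 13. The added tables, with their mirror images, are:

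| Active vs placebo | Fisher p | Boschloo p |
|---|---|---|
| 6/14 vs 0/7 | 0.061 | 0.037 |
| 9/14 vs 1/7 | 0.063 | 0.045 |
| 11/14 vs 2/7 | 0.056 | 0.030 |
| 13/14 vs 4/7 | 0.088 | 0.0475 |

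As a check on one Fisher value, 9/14 vs 1/7 gives (14,014 + 1,001 + 364 + 7,007)/352,716 = 0.0635.

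At 7 vs 7 the added table is 4/7 vs 0/7 (Fisher 2 × 35/1,001 = 0.070; Boschloo 0.024), with 7/7 vs 3/7 and the mirror images. At both sizes no table rejected by Fisher is lost.

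| | Fisher maximum size | Boschloo maximum size |
|---|---|---|
| 14 vs 7 | 2.21% | 4.75% |
| 7 vs 7 | 1.29% | 2.37% |

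These are maxima. At a common response rate of 20%, Fisher's level is 1.54% (14 vs 7) and 0.22% (7 vs 7).

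**Power at assumed rates (active vs placebo).**

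| Sizes | Rates | Fisher | Boschloo | Gain, points |
|---|---|---|---|---|
| 14 vs 7 | 70% vs 20% | 46.7% | 59.9% | 13.2 |
| 14 vs 7 | 70% vs 30% | 28.7% | 40.3% | 11.6 |
| 14 vs 7 | 70% vs 40% | 16.1% | 24.6% | 8.5 |
| 14 vs 7 | 80% vs 20% | 67.6% | 78.1% | 10.5 |
| 14 vs 7 | 90% vs 10% | 96.5% | 98.3% | 1.8 |
| 7 vs 7 | 70% vs 20% | 27.9% | 33.6% | 5.7 |

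Hand check of the first row: the four added tables contribute 0.0232×0.2097 + 0.1963×0.3670 + 0.1943×0.2753 + 0.0407×0.0287 = 0.0049 + 0.0720 + 0.0535 + 0.0012 = 0.1316, or 13.2 points.

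Over a grid of placebo 10–50%, active 50–90% and a difference of at least 30 points, the gain runs from 1.8 to 13.6 points at 14 vs 7 (median 10.5) and from 2.2 to 14.0 at 7 vs 7 (median 6.1).

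**The case against.** Fisher's test is standard and valid at small sizes, and the protocol already names it. A reader might infer from the low attained size that the SAP mishandles type I error. It does not: the test errs on the safe side, and the only loss is power. That part of the defence stands in full.

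A reader might also take the gain for H06 to be 12 to 13 points. The documents do not support a single figure. It needs placebo near 20–25% and active near 70%, rates that appear nowhere in the plan, and it needs H06 read as pooled. The phrase naming 680 or 340 mg does not settle that reading. If one dose is meant, the gain at 70% vs 20% is 5.7 points, and even Boschloo attains only 2.4%.

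It is also tempting to extend the change to SAP 9.4.2. That section tests seven thresholds on three scales at all timepoints, for each dose against placebo, with no adjustment. A test that uses more of its alpha would there also produce more false positives, so the argument does not carry over.

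Finally, H06 comes last in a fixed sequence. MG-ADL is tested on its percentage change first (H05), and logistic regression supports the responder analysis. The gain therefore counts only when the earlier steps succeed. This limits the weight of the point but does not remove it.

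**Conclusion.** The point holds as a cheap improvement to a valid plan. At the planned sizes, Fisher's test for H06 has a maximum size of 2.2% (pooled) or 1.3% (one dose) against the 5% allotted. Boschloo's test stays within 5% at both sizes and is never less powerful.

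The sizes and the absence of any power loss rest only on the planned numbers; they shift with the final counts (at 13 vs 7, Fisher's maximum is 2.06%). The size of the gain rests on assumed response rates and on how H06 is read: about 2 to 14 points over the grid for 14 vs 7, and about 6 points for 7 vs 7 at 70% vs 20%.

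**What to change.** Before unblinding:

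1. In SAP 9.3, name one test for H06: Boschloo's two-sided exact unconditional test, with tables ordered by the two-sided Fisher p-value. The version must be stated. Doubling a one-sided Boschloo p-value gives 0.091 for 13/14 vs 4/7, where the ordering above gives 0.0475.
2. In SAP 9.2, state whether H06 is the pooled active arms against placebo or a single dose.
3. Keep Fisher's test for H06 as a stated sensitivity analysis, with its p-value shown beside the primary one.
4. List the departure from protocol 10.3.2 in SAP section 14.
5. Leave the unadjusted secondary responder tests in SAP 9.4.2 with Fisher, and say that the H06 result comes from the test named in 9.3.

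The cost is SAP wording and a few lines of code. The downsides are a test that some readers know less well, and fuller use of the 5% error allowance at this step.

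### SAP 9.4.2 lets an unadjusted 0.05 confer significance on undefined component scores and on MG-ADL outcomes that SAP 9.2 gates; these p-values should be labelled nominal

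*SAP*

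**What the plan says.** SAP 9.4.2 takes the "Total MG-ADL, QMG, MGC, and MG-QoL15r score and each of the component scores", summarises them, and fits an ANCOVA with treatment and baseline to them. It adds: "The least-squares means will be compared using a t-test". The section closes on multiplicity: "There will be no adjustments for multiple comparisons for secondary endpoints. An alpha level of 0.05 will determine statistical significance". SAP 5.4 also rules out adjustment: "There will be no adjustments for multiple comparisons for the secondary efficacy or OLE endpoints".

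SAP 9.4.1 defines the change-score endpoints by visit, for example "Change from baseline in the QMG score by visit through Week 7". It describes each scale as a sum of items: 13 for QMG, 10 for MGC, 8 for MG-ADL and 15 for MG-QOL15r. Neither the protocol's objectives and endpoints nor SAP 9.4.1 lists a single item as an endpoint.

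SAP 9.2 sets an ordered sequence of hypotheses: total IgG, anti-AChR-IgG, percent change in MG-ADL, then MG-ADL responders. Under SAP 5.4 testing stops at the first non-significant result. SAP 3 says that this sequencing controls alpha and that nothing further is required. QMG, MGC, MG-QOL15r and the items are outside the sequence.

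**The concern.** Two things in SAP 9.4.2 do not fit the rest of the plan.

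First, the significance rule has no qualifier and sits over a very large set of tests. Many of them concern quantities that no endpoint list names. The protocol's OLE section, by contrast, says its 0.05 tests are informational.

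Second, MG-ADL is tested in two places. If the SAP 9.2 sequence stops before MG-ADL, those hypotheses should not be declared significant. SAP 9.4.2 nevertheless tests MG-ADL change and response at 0.05 and lets that level settle significance. That weakens the statement in SAP 3.

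The study rationale in the protocol (3.2.1) says the results will support moving to a larger and longer study to confirm efficacy. A chance finding on one item, or an MG-ADL result that bypassed the gate, could enter that decision labelled as statistically significant.

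**Working it through.** **The plan's own figure.** The documents give no family-wise error rate for the secondary tests, so there is none to reproduce. The power statement in SAP 1.3 concerns total IgG only; it is used here just for the arm sizes.

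**Inputs from the documents**
- Outcomes (SAP 9.4.1 and 9.4.2): 4 totals; items 8 + 13 + 10 + 15 = 46; together 50.
- Comparisons: each dose against placebo, so 2 per outcome. This comes from Protocol 10.3.2; the ANCOVA paragraph of SAP 9.4.2 does not state it.
- Arm size: 14 active and 7 placebo, randomised 1:1:1, so 7 per arm.
- Alpha: 0.05 per test.

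**Assumptions:** two-sided tests (SAP 9.3 says so for the primary analysis), Week 7 only, no treatment effect, component scores read as items, and the correlations below.

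**Step 1: number of tests.** Totals: 4 × 2 = 8. Totals and items: 50 × 2 = 100.

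**Step 2: expected false positives, whatever the correlation.** 8 × 0.05 = 0.4 and 100 × 0.05 = 5.

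**Step 3: chance of at least one if independent.** 1 − 0.95^8 = 33.7% and 1 − 0.95^100 = 99.4%.

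**Step 4: correlated outcomes, simple model.** Normal outcomes with one common correlation, three arms of 7, pooled-variance t-tests, no baseline covariate:

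| Correlation | 8 tests, either direction | 100 tests, either direction | 100 tests, favouring drug |
|---|---|---|---|
| 0.3 | 29% | 95% | 64% |
| 0.5 | 27% | 84% | 48–49% |
| 0.7 | 23% | 62–63% | 33% |
| 0.9 | 16–17% | 33% | 17% |

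**Step 5: closer to the planned analysis.** ANCOVA with each outcome's own baseline, totals built as sums of their items, and correlation within scales slightly higher than between them. The first figure is for continuous items, the second for items with four levels:

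| Within-scale correlation | 8 tests, either direction | 100 tests, either direction | 100 tests, favouring drug |
|---|---|---|---|
| 0.2 | 27% / 29% | 98% / 98% | 76% / 78% |
| 0.4 | 23% / 27% | 95% / 96% | 64% / 64% |
| 0.6 | 20% / 22% | 83% / 90% | 48% / 54% |
| 0.8 | 18% / 19% | 60% / 76% | 31% / 42% |
| 0.9 | 14% / 18% | 39% / 63% | 19% / 31% |

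The two models agree closely, and discrete items do not weaken the result.

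**Step 6: earlier visits.** If all four scales had five post-baseline visits (a simplification), the chance for the totals would be 50–83%, and with the items 87–100%. These figures are outside the Week 7 size given in the verdict.

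**Step 7: MG-ADL in the two sections.** SAP 9.2 gates percent change in MG-ADL and the MG-ADL responder proportion. SAP 9.4.1 lists MG-ADL change by visit and a response of at least 2 points at Week 7, and SAP 9.4.2 tests both without a gate. Percent change and change in points are closely related rather than identical; for response the outcome is essentially the same. Suppose the sequence stops at anti-AChR-IgG. SAP 5.4 then ends testing, while SAP 9.4.2 still allows MG-ADL response to be called significant at 0.05.

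**The case against.** The strongest reply is that this is a disclosed choice in a small Phase 2a trial. Two SAP sections say secondary endpoints are unadjusted, the sample size was not set by statistical methods, the primary objectives are safety and IgG, and efficacy is left to a later study. That stands: absence of adjustment is not a defect here, and no alpha correction is asked for.

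Several textual replies also have force.
- Component scores is undefined, so reading it as all 46 items is an inference. The SAP defines no other subscore, which makes it the natural reading, but the text does not say it.
- If items are not secondary endpoints, a literal reader could say that the 0.05 rule does not reach them. Yet they are tested in the same paragraph of the same section, and no other rule is given for them there. The body of SAP 9.5 is not in the public copy, so any label there cannot be checked.
- MG-ADL is partly handled by the SAP 9.2 sequence. That is true, and it is why the second, ungated test matters.

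Stronger readings are tempting but not supported.
- A reader might infer that a false claim is likely even on the totals. At Week 7 the chance is about 14–34%.
- A reader might take the figure above 80% as the chance of a false improvement. It counts both directions; the drug-favouring figure is about 48%.
- A reader might suppose that the protocol names Week 7 totals as endpoints. Its list gives these scores no timepoint; Week 7 comes from the SAP and from the timing of the primary analysis.

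**Conclusion.** The concern holds as a matter of labelling and consistency. SAP 9.4.2 attaches an unqualified significance rule to component scores that no endpoint list contains, and to MG-ADL outcomes that SAP 9.2 gates.

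At Week 7 under no effect, the chance of at least one significant result in either direction is about 14–34% for the four totals. With 46 items added it is just over 80% at an assumed correlation of 0.5, and about 33–98% over correlations of 0.9 to 0.2. Counting only results that favour the drug, it is about 48% (about 17–78%). The expected 5 false positives among 100 tests do not depend on the correlation. The item figures rest on component scores meaning items, two separate dose comparisons and 7 per arm; the correlations are assumed.

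The MG-ADL inconsistency needs none of these assumptions. Nothing here affects the total IgG analysis or suggests that the lack of adjustment was concealed.

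**What to change.** In SAP 9.4.2:
- Replace the significance sentence with a statement that secondary p-values are nominal and support no claim of statistical significance, except for hypotheses reached in the SAP 9.2 sequence.
- State that an MG-ADL hypothesis not reached in that sequence cannot be declared significant under 9.4.2.
- Define component scores, and present them with estimates and 95% CIs, without significance statements.
- Keep the by-visit totals as the secondary endpoints that SAP 9.4.1 defines, with 95% CIs and nominal p-values.

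The cost is SAP wording, with no extra patients and no loss of data. The small downside is that items and ungated scores can no longer be reported in significance language.
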